## 8.0 SAFETY AND ADVERSE EVENTS

### 8.1 Recording of Adverse Events

At each contact with the subject, the investigator will seek information on adverse events by specific questioning and, as appropriate, by examination. Information on all adverse events will be recorded immediately in the source document. All clearly related signs, symptoms, and abnormal diagnostic procedures results will also be recorded in the source document.

All adverse events will be immediately reported to the primary investigators and to the IRB, per their procedures. The clinical course of each event will be followed until resolution, stabilization, or until it has been determined that the study treatment or participation is not the cause. Serious adverse events that are still ongoing at the end of the study period will be followed up to determine the final outcome. Any serious adverse event that occurs after the study period and is considered to be possibly related to the study treatment or study participation will be recorded and reported immediately.

## 8.2 Serious/Unexpected Adverse Events

Serious and unexpected adverse events will be reported to the Ethical Committee in accordance with institutional guidelines. In the case there would be any adverse events or unanticipated problems, an appropriate adverse event or unanticipated report form will be made and the Ethical Committee notified immediately. The study will also be stopped immediately if a subject would experience any unanticipated discomfort or adverse cardiac events (e.g. hospitalization). There will be no DMC and no interim analyses.

## 9.0 DATA HANDLING AND RECORD KEEPING

### 9.1 Confidentiality and Privacy

Information about study subjects will be kept confidential and managed according to the Health Insurance Portability and Accountability Act of 1996 (HIPAA). Subjects will be informed of their rights and the privacy safeguards in place during the consent process.

### 9.2 Data Management

Study data will be collected and managed using REDCap (Research Electronic Data Capture). REDCap is a secure, web application designed to support data capture for research studies, providing user-friendly web-based case report forms, real-time data entry validation (e.g. for data types and range checks), audit trails and a de-identified data export mechanism to common statistical packages (SPSS, SAS, Stata, R/S-Plus). The system was developed by a multi-institutional consortium which includes Cleveland Clinic and was initiated at Vanderbilt University. The database is hosted at the Cleveland Clinic Datacenter. The system is protected behind a login and Secure Sockets Layer (SSL) encryption. There is an audit trail tracking all logins and activities in the database. Data collection is customized for each study or clinical trial based on a

study-specific data dictionary defined by the research team with guidance from the REDCap administrator in Quantitative Health Sciences at the Cleveland Clinic.

### 9.3 Records Retention

All source documents, including the case report forms, will be kept for at least 6 years following the completion of the study. Documents will be stored in a secure location with limited access.

## **10.0 STUDY MONITORING, AUDITING AND INSPECTING**

### 10.1 Study Monitoring

The Investigator will ensure that any monitor or other compliance or quality assurance reviewer is given access to all study-related documents and study related facilities, and that they have adequate space to conduct the monitoring visit.

### 10.2 Auditing and Inspecting

The investigator will permit study-related monitoring, audits, and inspections by the IRB, the sponsor, government regulatory bodies, and Institutional compliance and quality assurance groups of all study related documents (for example, source documents, regulatory documents, data collection instruments, study data etc.). The investigator will ensure the capability for inspections of applicable study-related facilities (for example, pharmacy, diagnostic laboratory, etc.). Participation as an investigator in this study implies acceptance of potential inspection by government regulatory authorities and applicable Institutional compliance and quality assurance offices.

## **11.0 ETHICAL CONSIDERATIONS**

This study will be conducted according to US and international standards of Good Clinical Practice (FDA Title 21 part 312 and International Conference on Harmonization guidelines), applicable government regulations and Institutional research policies and procedures.

This protocol and any amendments will be submitted to a properly constituted independent Institutional Review Board (IRB), in agreement with local legal prescriptions, for formal approval of the study conduct. The decision of the IRB

concerning the conduct of the study will be made in writing to the investigator before commencement of this study.

## **Study Overview**

The overall purpose of the study COSETTE (Consumption of Oral Artificial Sweeteners on Platelet Aggregation and Polyol Excretion) is to develop a clinical protocol for performance of pilot studies aimed at exploring both changes in blood levels observed following ingestion of a polyol, and its potential impact on platelet function. The initial studies will focus on two polyols that are currently used as artificial sweeteners – erythritol, and xylitol. Studies will proceed focusing individually on each compound sequentially, with studies on each compound being independent of the other. Subject enrolment will proceed for one polyol at a time. COSETTE will thus serve as a template that is to be applied to one compound at a time.

### **Background:**

Erythritol and xylitol are both polyols (compounds with 2 or more hydroxyl groups) found in fruits and vegetables in low amounts. They are widely used artificial sweeteners by the food industry. Due to a sweetening intensity comparable to that of sucrose but lower calorie content erythritol and xylitol are added in large quantities into processed food. Since they do not raise insulin levels and have little to no effect on blood glucose levels, both polyols are also attractive for the use as sugar alternatives in patients with cardiometabolic diseases, such as type 2 diabetes.

Both mentioned sweeteners are generally considered safe and approved by the Food and Drug Administration (FDA). Major side effects of excessive consumption comprise flatulence, laxation, and headache. Erythritol and xylitol are well tolerated up to an intake of 60g and 50g daily, respectively

Up to now, there is no prospective data available about polyols with respect to their impact on event outcomes in cardiovascular patients, despite the extensive use in the food industry. Moreover, little is known about plasma levels and metabolic changes following food intake of artificial sweeteners, in particular polyols.

We have measured fasting levels of various polyols in a large clinical cohort of cardiovascular patients and found that some candidate polyols are related to a higher risk of cardiovascular complications and death. *In vitro* data using human platelets revealed that the polyols xylitol and erythritol at the levels observed in fasting patients enhance platelet aggregation potential. Our data shows that erythritol and xylitol, impact platelet function and thereby may contribute to cardiovascular mortality.

This Statistical analysis plan is based upon the following study documents:

### **Study Objective**

The principal goal for the study is to examine whether ingestion of a beverage containing artificial sweeteners alters *in vitro* platelet function. Post prandial levels of polyols following ingestion will also be assessed. We will focus on two popular artificial sweeteners: erythritol and xylitol.

#### **Study Aims**

- 1. To assess post prandial levels of erythritol and xylitol following ingestion of 30g dissolved in water
- 2. To assess indices of platelet function following erythritol and xylitol ingestion

### **Study Hypothesis**

- 1. We hypothesize that polyol concentrations in the blood (erythritol and xylitol) increase following ingestion.
- 2. We hypothesize that post prandial levels of polyols (erythritol and xylitol) alter platelet function.

## **Study Design**

We will perform a prospective, non-blinded, 2-arm, parallel design study with subjects allocated to receive either erythritol or xylitol as their intervention.

At baseline, subjects will have blood and urine samples collected. Subjects will then receive a drink (300mL of water containing up to 30g of erythritol or 30g of xylitol) as a single oral dose. We will use the Now Foods brand of each sweetener and plan to obtain both sweeteners from a commercial source (e.g. Amazon.com or a local pharmacy). Blood and urine samples will be collected again 30 minutes after ingestion (and at time points indicated in the tables below) of the sweetened water drink.

### Xylitol arm schedule:

	Visit 1 Day 1	Visit 2 Day 2
Informed Consent	Χ	
Brief Medical History Questionnaire	Х	
Vital Signs	Х	
Baseline Fasting Blood Collection	Х	Х
Baseline Fasting Urine Sample	Х	Х
Drink Sweetened Water	Х	
30 minutes Post-drink Blood & Urine Collection*	Х	
1 hour Post-drink Blood & Urine Collection*	Х	
4 hours Post-drink Blood & Urine Collection*	Х	
6 hours Post-drink Blood & Urine Collection*	X	

# Erythritol arm schedule:

	Vital Signs	Medical History	Blood Draw	Spot Urine Sample
Baseline	Х	Х	X	Х
+ 30 minutes			Х	Х
+ 2 hours*			Х	Х
+ 6 hours*			Х	Х
+ 24 hours (Day 2)*			Х	Х
+ 48 hours (Day 3)*			Х	X
+ 72 hours (Day 4)*			Х	X
+ 96 hours (Day 5)*			Х	X
+ 168 hours (Day 8)*			Х	Х
+ 216 hours (Day 10)*			Х	Х

+ 264 hours (Day 12)*	Х	X

\*Laboratory schedules are subject to change as data is gathered. Subjects will be informed of lab schedule at time of consent.

### **Subject Compliance Monitoring**

Subjects will be observed taking their assigned intervention, either erythritol or xylitol solution, by a study coordinator or other study personnel during their visit to ensure the subjects are able to comply with the study procedures.

## **Study Population**

There will be 2 different cohorts

#### Cohort 1 Inclusion Criteria

- Men and women age 18 years or above.
- Able to provide informed consent and comply with study protocol.

#### Cohort 1 Exclusion Criteria

- · Use of anti-platelet medications within 14 days of study enrollment.
- Active infection or received antibiotics within 1 month of study enrollment.
- Use of OTC probiotic within 1 month of study enrollment.
- · Diabetes Mellitus
- Ulcerative colitis, Crohn's disease, or other chronic gastrointestinal disorder.
- Past history of bariatric procedures or surgeries (e.g. gastric banding or bypass).
- Pregnancy.
- Significant chronic illness.

• Any condition that, in the judgment of the Investigator, would place a subject at undue risk by being enrolled in the trial or cause inability to comply with the trial.

#### Cohort 2 Inclusion Criteria

- Men and women age 18 years or above.
- Able to provide informed consent and comply with study protocol.
- Diabetes Mellitus Type II

#### Cohort 2 Exclusion Criteria

- Use of anti-platelet medications within 14 days of study enrollment.
- Active infection or received antibiotics within 1 month of study enrolment.
- Use of OTC probiotic within 1 month of study enrolment.
- Ulcerative colitis, Crohn's disease, or other chronic gastrointestinal disorder.
- Past history of bariatric procedures or surgeries (e.g. gastric banding or bypass).
- Pregnancy.
- Any condition that, in the judgment of the Investigator, would place a subject at undue risk by being enrolled in the trial or cause inability to comply with the trial.

## **Subject Recruitment and Screening**

Subjects will be recruited from the Cleveland, OH area. Subjects will be recruited by several methods, including (but not limited to) posted advertisements, chart review, and personal interactions with patients in the cardiology outpatient departments at the Cleveland Clinic Foundation. All advertising materials used for this study will be approved by the Cleveland Clinic IRB prior to dissemination.

#### **Subject Consent**

Written consent will be obtained from all subjects prior to any study procedure being performed. Participants will be provided with a copy of the signed consent form. Consent will also be documented in the subject's medical record in EPIC.

### **Early Withdrawal of Subjects**

Subjects may withdraw from the trial at any time and for any reason. Some possible reasons for early withdrawal include the following:

- Development of a medical condition or need for concomitant treatment that precludes further participation in the trial
- Removal from the trial by the investigator in the best interests of the subject
- Development of an active infection or starting an antibiotic treatment regimen
- Study completion or discontinuation prior to participant completion
- · Subject withdraws consent to continued participation in the trial

## **Recording of Adverse Events**

At each contact with the subject, the investigator will seek information on adverse events by specific questioning and, as appropriate, by examination. Information on all adverse events will be recorded immediately in the source document. All clearly related signs, symptoms, and abnormal diagnostic procedures results will also be recorded in the source document.

All adverse events will be immediately reported to the primary investigators and to the IRB, per their procedures. The clinical course of each event will be followed until resolution, stabilization, or until it has been determined that the study treatment or participation is not the cause. Serious adverse events that are still ongoing at the end of the study period will be followed up to determine the final outcome. Any serious adverse event that occurs after the study period and is considered to be possibly related to the study treatment or study participation will be recorded and reported immediately.

#### Serious/Unexpected Adverse Events

Serious and unexpected adverse events will be reported to the Ethical Committee in accordance with institutional guidelines. In the case there would be any adverse events or unanticipated problems, an appropriate adverse event or unanticipated report form will be made and the Ethical Committee notified immediately. The study will also be stopped immediately if a subject would experience any unanticipated discomfort or adverse cardiac events (e.g. hospitalization). There will be no DMC and no interim analyses.

### **Data Management**

Study data will be collected and managed using REDCap (Research Electronic Data Capture). REDCap is a secure, web application designed to support data capture for research studies, providing user-friendly web-based case report forms, real-time data entry validation (e.g. for data types and range checks), audit trails and a de-identified data export mechanism to common statistical packages (SPSS, SAS, Stata, R/S-Plus). The system was developed by a multi-institutional consortium which includes Cleveland Clinic and was initiated at Vanderbilt University. The database is hosted at the Cleveland Clinic Datacenter. The system is protected behind a login and Secure Sockets Layer (SSL) encryption. There is an audit trail tracking all logins and activities in the database. Data collection is customized for each study or clinical trial based on a study-specific data dictionary defined by the research team with guidance from the REDCap administrator in Quantitative Health Sciences at the Cleveland Clinic.

### **Outcomes**

### **Primary Outcomes**

- Polyol levels (erythritol and xylitol) in the blood quantified using established techniques by mass spectrometry.
- Polyol levels (erythritol and xylitol) in the urine quantified using established techniques by mass spectrometry.
- · changes in platelet function throughout the study using well established in vitro platelet assays

### **Secondary Outcomes**

• Changes in markers of metabolism

# **Sample Size Determination**

Based on previous research, we calculate that a sample size of 10 will provide us with a power of 0.9 to detect a significant difference between groups at a significance level of 0.05. However, we plan to enrol at least 15 subjects in each cohort in each arm in order to compensate for any unexpected occurrences or subject dropouts.

## **Demographic and Clinical Characteristics**

We plan to use standard descriptive statistics to characterize the overall study population of interest both at baseline and during follow-up. Summary statistics of demographic variables (e.g. age, self-reported race and ethnicity), such as means, medians, standard deviations, and ranges will be produced for measured variables, and compared within and between groups with chi-square, Student t-test/Wilcoxon test, or ANOVA analysis as appropriate.

## Statistical analysis Plan for Primary outcomes

- Erythritol concentration in the blood at various time points will be analyzed by ANOVA analysis or Student t-test/Wilcoxon test as
  appropriate. Type I error will be controlled for though adjustment for multiple testing as appropriate. A P value <0.05 will be considered
  significant.

- 2. Erythritol concentration in the urine at various time points will be normalized to urine creatinine levels: erythritol urine/ creatinine urine. Levels will be analyzed by ANOVA analysis or Student t-test/Wilcoxon test as appropriate. Type I error will be controlled for though adjustment for multiple testing as appropriate. A P value <0.05 will be considered significant.
- 3. Platelet functional changes before and after xylitol/erythritol drink will be analyzed by ANOVA analysis or Student t-test/Wilcoxon test as appropriate. Type I error will be controlled for though adjustment for multiple testing as appropriate. A P value <0.05 will be considered significant.

# Statistical analysis Plan for Secondary outcomes

1. Changes in metabolic markers at various time points will be by ANOVA analysis or Student t-test/Wilcoxon test as appropriate. Type I error will be controlled for though adjustment for multiple testing as appropriate. A P value <0.05 will be considered significant.

# **Hypothesis testing**

For aim 1, we will test the hypothesis that post prandial levels of erythritol or xylitol (after 30g ingestion) exceed fasting levels. Testing will be performed by comparing post prandial erythritol levels with fasting levels in each individual.

For aim 2, we will test the hypothesis that post prandial levels of erythritol and xylitol alter platelet function. Testing will be performed by comparing markers for platelet function before and after exposure to xylitol or erythritol.

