In preliminary studies we found that upon ingestion erythritol and xylitol levels in the plasma rise within the first hour. With this study we wish to examine whether the postprandial levels are capable of altering platelet function *in vitro*. We hypothesize that post prandial polyol concentrations following ingestion increase platelet aggregation in the blood.

Glucose, as a naturally occurring sweetener, will serve as a control for this study. There is also evidence that glucose may increase platelet aggregation, allowing us to compare the degree of increased aggregation between the polyol sweeteners and glucose. (3)

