## 3.0 STUDY DESIGN

We will perform a prospective, non-blinded, 4-arm study. There will be up to 8 study visits depending on which arm the subject is assigned to. There will be three interventions: erythritol, xylitol, and glucose. Erythritol and glucose will each be used in one arm, xylitol will be used in two arms.

At baseline, subjects will have fasting blood and urine samples collected. Subjects will then receive a drink (300mL of water containing either 30g of erythritol, 30g of xylitol, 5g of xylitol, or 30g of glucose) as a single oral dose. Blood and urine samples will be collected again on the same day at pre-determined intervals after ingestion of the sweetened water drink. Additional fasting blood and urine samples may be collected on subsequent days after drinking the artificially sweetened water as shown in the tables below. Subjects drinking xylitol (5g or 30g) may have 1 subsequent visit. Subjects consuming erythritol may have up to 7 subsequent visits. Subjects consuming glucose will have 1 study visit with blood and urine being collected about 30 minutes apart. All fasting collections will occur after an 8+ hour fast.

Xylitol schedule (5g and 30g):

	Visit 1 Day 1	Visit 2 Day 2
Informed Consent	X	
Brief Medical History Questionnaire	X	
Vital Signs	X	

Baseline Fasting Blood Collection	X	X
Baseline Fasting Urine Sample	X	X
Drink Sweetened Water	X	
30 minutes Post-drink Blood & Urine Collection*	X	
1 hour Post-drink Blood & Urine Collection*	X	
4 hours Post-drink Blood & Urine Collection*	X	
6 hours Post-drink Blood & Urine Collection*	X	

Erythritol schedule:

	Vital Signs	Medical History	Blood Draw	Spot Urine Sample
Baseline	X	X	X	X
+ 30 minutes			X	X
+ 2 hours*			X	X
+ 6 hours*			X	X
+ 24 hours (Day 2)*			X	X
+ 48 hours (Day 3)*			X	X
+ 72 hours (Day 4)*			X	X
+ 96 hours (Day 5)*			X	X
+ 168 hours (Day 8)*			X	X
+ 216 hours (Day 10)*			X	X
+ 264 hours (Day 12)*			X	X

Glucose schedule:

	Vital Signs	Medical History	Blood Draw	Spot Urine Sample
Baseline	X	X	X	X
+ 30 minutes			X	X

\* Laboratory schedules are subject to change as data is gathered. Subjects will be informed of lab schedule at time of consent.

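### The SAP's platelet test is before/after within each polyol arm, with no inert comparator and no specified contrast with glucose, so it cannot separate a polyol effect from time or procedure effects

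*SAP*

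**What the plan says.** Under Hypothesis testing, the SAP decides aim 2 as follows: "Testing will be performed by comparing markers for platelet function before and after exposure to xylitol or erythritol". Item 3 of its analysis plan for primary outcomes agrees: "Platelet functional changes before and after xylitol/erythritol drink will be analyzed by ANOVA analysis or Student t-test/Wilcoxon test as appropriate". Neither names a comparator arm.

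The two documents describe different sets of arms. SAP, Study Design: "We will perform a prospective, non-blinded, 2-arm, parallel design study with subjects allocated to receive either erythritol or xylitol as their intervention". Protocol 3.0: "Erythritol and glucose will each be used in one arm, xylitol will be used in two arms". The glucose and 5 g xylitol arms are thus missing from the SAP.

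On the role of glucose, Protocol 1.0 says: "Glucose, as a naturally occurring sweetener, will serve as a control for this study". It continues: "There is also evidence that glucose may increase platelet aggregation, allowing us to compare the degree of increased aggregation between the polyol sweeteners and glucose". Under Protocol 3.0 and 4.0 the glucose arm takes healthy subjects only and is sampled at baseline and about 30 minutes later. Protocol 7.2 allows comparisons within and between groups in general terms, without naming one for platelet function.

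**The concern.** A before/after difference contains everything that changes between the fasting draw and the post-drink draw: the sweetener, 300 mL of fluid, a repeat draw, clock time and assay variation. Nothing in the specified test removes the non-sweetener part.

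The glucose arm could help, but the SAP does not use it, and the protocol says glucose may be active. If polyol and glucose changes were equal, both could be active, or both could be procedural.

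At stake is the SAP's stated principal goal. A significant result under the rule as written shows that the marker changed after the drink; it does not show that the polyol changed it.

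**Working it through.** **The plan's own figures.** Protocol 7.1 and the SAP give 10 subjects, power 0.9 and significance level 0.05 for a difference between groups. No effect size, SD, outcome, sidedness or unit is stated, so the 10 can only be back-solved. With two-sided t-tests it implies a standardised effect of 1.15 if it means 10 pairs, or 1.53 if it means 10 per group. The enrolment cap in Protocol 6.0 does reproduce: (3 polyol arms × 2 cohorts + 1 glucose group) × 15 = 105. The completer goal is 12 per polyol cohort and 12 on glucose.

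**False attribution under the before/after rule.** Assume no polyol effect and a non-sweetener shift of d SDs of the within-subject change. The paired two-sided 0.05 test rejects with probability P(|T| > t), where T is noncentral t with n − 1 degrees of freedom and noncentrality d√n. The critical t is 2.201 at n = 12 and 2.145 at n = 15.

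| Assumed shift d | n = 12: d√n | n = 12: P(reject) | n = 15: d√n | n = 15: P(reject) |
|---|---|---|---|---|
| 0 | 0 | 0.05 | 0 | 0.05 |
| 0.3 | 1.04 | 0.158 | 1.16 | 0.192 |
| 0.5 | 1.73 | 0.353 | 1.94 | 0.438 |
| 0.8 | 2.77 | 0.714 | 3.10 | 0.821 |

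**Comparators the protocol already provides.** The 30-minute draw is the only post-drink time shared by all four arms.

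| Group | Comparator at 30 minutes |
|---|---|
| Erythritol, non-diabetic | glucose |
| Erythritol, diabetic | none |
| Xylitol 30 g, non-diabetic | glucose; xylitol 5 g |
| Xylitol 30 g, diabetic | xylitol 5 g |

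**Power of a between-arm contrast of change.** Assume equal SDs of change in both arms, a polyol effect of 1.15 SD (the 10-pairs reading), and a comparator that shows a fraction f of that effect. The noncentrality is 1.15(1 − f)√(n/2), with 2n − 2 degrees of freedom. At n = 12 per arm and f = 0 this is 1.15 × 2.449 = 2.83 (unrounded effect 1.155) against a critical t of 2.074.

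| f | Power, 12 per arm | Power, 15 per arm | n per arm for 90% |
|---|---|---|---|
| 0 | 0.77 | 0.86 | 17 |
| 0.25 | 0.53 | 0.63 | 30 |
| 0.5 | 0.27 | 0.33 | 65 |

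The paired test at the same effect has power 0.95 with 12. On the 10-per-group reading (1.53 SD), between-arm power with 12 per arm is 0.95, 0.77 and 0.44 for f = 0, 0.25 and 0.5.

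**Precision.** With 12 per arm, the 95% half-width is about 2.074 × √(2/12) = 0.85 SD for the between-arm difference, against 2.201/√12 = 0.64 SD for the paired change.

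**If the shift is not common to both arms.** Should the arms' non-sweetener shifts differ by 0.3, 0.5 or 0.8 SD (assumed), the two-sample test with 12 per arm falsely rejects 11%, 22% or 47% of the time.

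**The case against.** The strongest reply is that the protocol has already thought of this. It intends to compare the degree of aggregation with glucose, allows between-group tests, and its sample-size text speaks of groups. Platelet function is followed through later draws alongside measured polyol levels, so a return towards baseline would give some within-subject support. It is a pilot, and the shift sizes above have no source in the documents; 0.8 SD is not small.

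Much of this stands, and it limits the point. But the intention in Protocol 1.0 never becomes a named contrast in either document, and the SAP has no glucose arm to contrast with. A return to baseline is also what a transient fluid or time-of-day effect would produce.

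A reader might infer four stronger things that the documents do not support:

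- That the protocol expects glucose to raise aggregation. It says only that it may.
- That no platelet change could ever be attributed to a polyol. If glucose does raise aggregation, an excess over glucose at 30 minutes in non-diabetic subjects would still be some evidence for the polyol.
- That xylitol 30 g versus 5 g should be the deciding test and would hold the error rate at 0.05. Protocol 1.0 reports platelet effects of xylitol at levels seen in fasting patients, so 5 g may be active too. The SAP addendum records that randomisation between polyols was dropped, neither document describes random allocation among the four arms, and neither says the two xylitol arms run concurrently. A common shift therefore cannot be assumed to cancel.
- That the 5 g xylitol arm could set the threshold for erythritol. The SAP overview enrols one polyol at a time and treats the compounds as independent studies.

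**Conclusion.** The concern holds for the test as specified. The SAP's aim 2 analysis is an uncontrolled before/after comparison. It omits two of the protocol's arms and does not carry out the glucose comparison that the protocol intends. It cannot separate a polyol effect from time, fluid, repeat-draw or assay effects.

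The size depends on an unknown shift: over the assumed range of 0.3 to 0.8 SD, the chance of a false attribution is 0.16 to 0.71 at 12 completers and 0.19 to 0.82 at 15, against a nominal 0.05. The documents neither establish nor bound such a shift.

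Glucose is best read as an active comparator, available only in healthy subjects and only at 30 minutes. It gives no control for the diabetic cohort or for later draws. For a pilot this should be corrected, but it does not invalidate the study.

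**What to change.** 1. Reconcile the arms in SAP Study Design and Study Aims with Protocol 3.0, so that the analysis plan covers every arm that is enrolled.
2. In SAP Hypothesis testing (aim 2) and primary analysis item 3, keep the before/after test. Add estimates with 95% confidence intervals of the between-arm difference in platelet change from baseline at 30 minutes: each polyol arm minus glucose in the non-diabetic cohort, and xylitol 30 g minus 5 g within each cohort. Label them non-randomised and supportive.
3. State the reporting rule. A significant before/after change without an excess over a comparator arm is described as a change after the drink and is not attributed to the polyol. Define in advance what counts as an excess, for example a confidence interval that excludes zero. Erythritol in diabetic subjects has no comparator, so the limited wording applies there throughout.
4. State that similarity to glucose, or to the 5 g arm, is not evidence of no polyol effect, and call glucose an active comparator in Protocol 1.0.

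The cost is wording and analysis only, provided the 30-minute draw is kept in every arm; in the xylitol schedule it carries the footnote that allows changes. The downside is precision: power is about 0.77 at 12 per arm if the comparator is inert and the effect is the back-solved 1.15 SD, and 0.27 if the comparator shows half that effect. The contrasts may also be confounded by non-randomised, sequential enrolment, and they are conservative if the comparator is active.
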